16 DATA AND SAFETY MONITORING BOARD (DSMB)

The Coordinating Center currently has a DSMB that reviews the safety of all subjects enrolled in trials on an ongoing basis. The initial task of the DSMB will be to review the protocol to identify any necessary modifications. If modifications are necessary, revisions will be reviewed by the DSMB prior to its recommendation on initiation of the project. The DSMB, based on its review of the protocol, will work with the Medical and Safety Core personnel to identify the study-specific data parameters and format of the information to be regularly reported. The DSMB will initially be provided with data blinded to treatment status, but they may request unblinded data if there is a safety concern. The DSMB and NIA representative will meet in person or by conference call on a quarterly basis.

Additionally, the DSMB will be informed of the occurrence of any serious adverse events within 7 days of being reported to the Coordinating Center. The DSMB may at any time request additional information from the Coordinating Center.

Based on the review of safety data, the DSMB will make recommendations regarding the conduct of the study. These may include amending safety monitoring procedures, modifying the protocol or consent, terminating the study or continuing the study as designed. Using the ADCS

Safety Review Process (review of lab data, vitals, and adverse events) and the DSMB, there is substantial oversight and case review to alert the investigators, in a timely manner, to any safety issues that may arise. For further details, please refer to the DSMB charter.

Lastly, the DSMB will evaluate safety and tolerability for each dosing group.

17 RECORDING AND COLLECTION OF DATA

17.1 Case Report Form

The PI or designee will record all data collected (either written or electronic record of data). Written or electronic data of record must be entered on the eCRF provided for that purpose. In some instances, no prior written or electronic record of data may exist and data recorded directly on the eCRF is considered source data. The site will be suitably trained on the use of the eCRF and appropriate site personnel will be authorized to provide electronic signatures. The PI is responsible to verify the integrity of the data and acknowledge as such by signature.

All site entries will be made in a secured web site and the PI will review the record for completeness. If corrections are necessary to the eCRFs, the PI or designee will update the eCRF and provide documentation for the reason for change.

Completed eCRFs will be submitted according to provided instructions, and reviewed by the Coordinating Center to determine their acceptability. If necessary, data correction requests will be generated for resolution by the study site.

17.2 Study Files and Source Documents

Subject confidentiality is strictly held in trust by the participating investigators, research staff, and the Coordinating Center and/or sponsoring institution and their agents. This confidentiality is extended to cover testing of biological samples and genetic tests in addition to the clinical information relating to subjects.

The study protocol, documentation, data and all other information generated will be held in strict confidence. No information concerning the study or the data will be released to any unauthorized third party, without prior written approval of the sponsoring institution. Authorized representatives of the sponsoring institution may inspect all documents and records required to be maintained by the investigator, including but not limited to, medical records (office, clinic or hospital) and pharmacy records for the subjects in this study. The clinical study site will permit access to such records. Any data, specimens, forms, reports, video/audio recordings, and other records that leave the site will be identified only by a subject identification number (Subject ID, PID) to maintain confidentiality. All records will be kept in a locked file cabinet. All computer entry and networking programs will be done using PIDs only. Information will not be released without written permission of the subject, except as necessary for monitoring by the Institutional Review Board (IRB), the FDA, the NIA, and the Office for Human Research Protections (OHRP).

Information about study subjects will be kept confidential and managed according to the requirements of the Health Insurance Portability and Accountability Act (HIPAA) of 1996. Those regulations require a signed Subject HIPAA Authorization informing the subject of the following:

- What protected health information (PHI) will be collected from subjects in this study

- Who will have access to that information and why
- Who will use or disclose that information
- The rights of a research subject to revoke their authorization for use of their PHI

In the event that a subject revokes authorization to collect or use PHI, the investigator, by regulation, retains the ability to use all information collected prior to the revocation of subject authorization. Each site PI, under the guidance of his/her IRB, is responsible for ensuring that all applicable HIPAA regulations and State laws are met.

18 ETHICS AND REGULATORY CONSIDERATIONS

18.1 Good Clinical Practice

This study will be conducted in compliance with the protocol and accordance with Good Clinical Practice (GCP) guidelines, as defined by the International Conference on Harmonisation (ICH) Guideline, Topic E6, the United States Code of Federal Regulations (CFR), Title 21, Part 50 – Protection of Human Subjects, and Part 56 – IRBs, HHS Regulations (45 CFR part 46, 160, 164 HHS Regulations for the Protection of Human Subjects; HIPAA; 42 CFR part 50), Subpart F HHS Regulations for Responsibility of Applicants for Promoting Objectivity in Research for Which PHS Funding Is Sought HIPAA, State and Federal regulations and all other applicable local regulatory requirements and laws.

Study personnel involved in conducting this study will be qualified by education, training and experience to perform their respective task(s) in accordance with GCP.

No study document shall be destroyed without prior written agreement between the Coordinating Center and the investigator. Should the investigator wish to assign study records to another party or move them to another location, he/she may do so only with the prior written consent of the Coordinating Center.

18.2 Institutional Review Board (IRB)

Institutional Review Boards must be constituted and their authority delegated through the institution's normal process of governance according to applicable State and Federal requirements for each participating location. Each participating institution must provide for the review and approval of this protocol and the associated informed consent documents and recruitment material by an appropriate IRB registered with the OHRP. Any amendments to the protocol or consent materials must also be approved before they are placed into use. In the United States, only institutions holding a current US Federal wide Assurance (FWA) issued by OHRP may participate. Refer to: <http://www.hhs.gov/ohrp/assurances/>.

The investigator must obtain approval from the IRB for all subsequent protocol amendments and, when warranted, changes to the informed consent document. Protocol and informed consent form amendments can be made only with the prior approval of the Coordinating Center. The investigator may not implement any protocol deviation without prior notification, review, and documented approval from the ADCS, except where necessary to eliminate an immediate hazard to study subjects, or when change(s) involve only logistical or administrative aspects of the trial. The investigator shall notify the IRB of deviations from the protocol or serious adverse events occurring at the site, in accordance with local procedures.

18.3 Informed Consent and Health Insurance and Portability and Accountability Act (HIPAA) Compliance

Informed consent will be obtained in accordance with 21CFR§50.25, and ICH Good Clinical Practice. Applicable HIPAA privacy notifications will be implemented and HIPAA authorizations signed before protocol procedures are carried out. Information should be given in both oral and written form as deemed appropriate by the Site's IRB.

Prior to the beginning of the trial, the investigator must obtain the IRB's written approval of the informed consent form and any other written information to be provided to subjects and be acceptable by ADCS Regulatory Affairs. Consent forms must be in a language fully comprehensible to the prospective subjects and/or their authorized representatives and study partners. Subjects, their relatives, guardians, or authorized representatives and study partners will be given ample opportunity to inquire about the details of the study. Prior to a subject's participation in the trial, the written informed consent form must be signed and personally dated by the subject or by the subject's legally acceptable representative, and by the person who conducted the informed consent discussion. Subjects will be provided a copy of the signed ICF.

The informed consent will not only cover consent for the trial itself, but for the genetic samples/data/storage and biomarker samples/data/storage as well. Consent forms will specify that DNA and biomarker samples are for research purposes only; the tests on the DNA and biomarker samples are not diagnostic in nature and subjects will never receive results.

18.4 Genetic Research and Storage of Genetic Material

Only DNA from consenting subjects will be banked and used to facilitate future research on aging and dementia, particularly in the discovery of genetic polymorphisms that may influence risk of developing AD. Collection of DNA will permit investigators to probe candidate genetic polymorphisms as predictors of outcome in future studies. The samples will be stored by the ADCS as long as funding is available from the National Institutes of Health (NIH). If funding should lapse completely, the UCSD ADRC will provide responsible custodianship of the ADCS Biomarker Core.

18.5 Storage of Biospecimen Samples

All biospecimens being banked for future AD biomarker research will be shipped to and stored by the ADCS Biomarker Core. Sample tubes will be barcoded and inventoried by subject ID number only and banked without personal identifiers, in accordance with ADCS Biomarker Core SOPs. The presence of the sample is recorded into a computerized inventory database that is encrypted and password-protected.

Only specimens from consenting subjects will be banked and used to facilitate future research on aging and dementia. The samples will be stored by the ADCS as long as funding is available from the NIH. If funding should lapse completely, the UCSD ADRC will provide responsible custodianship of the ADCS Biomarker Core.

19 STUDY MONITORING

The clinical monitor is responsible for inspecting the online case report forms and source documentation at specific time points throughout the study to verify adherence to the protocol,

completeness and accuracy of the data, and adherence to local regulations on the conduct of clinical research. The monitoring visits must be conducted according to the applicable ICH and FDA guidelines to ensure protocol adherence, quality of data, drug accountability, compliance with regulatory requirements and continued adequacy of the investigational site and its facilities. The Site Investigator will cooperate in the monitoring process by ensuring the availability of the eCRFs, source documents and other necessary documents at the time of the monitoring visits. The Site Investigator will promptly address any matters brought to his/her attention by the monitor. The Site Investigator may also be asked to meet in-person with the site monitor during certain visits.

20 AUDIT

In accordance with ICH E6 (Good Clinical Practices) representatives of the Coordinating Center and/or Sponsor and/or regulatory agency may select this study for audit. The investigator and study staff are responsible for maintaining the site master file containing all study-related regulatory documentation as outlined by ADCS Regulatory Affairs that will be suitable for inspection at any time by ADCS, Sponsor, its designees, and/or regulatory agencies. Inspection of site facilities (e.g., pharmacy, laboratories) to evaluate the trial conduct and compliance with the protocol may also occur.

21 RECORD RETENTION

Essential documents and study records must be retained for a minimum of seven years following primary publication of study results. The Coordinating Center will notify sites when retention of such documents is no longer required. Essential documents should be retained for at least 2 years after the last approval of a marketing application in an ICH region and until there are no pending or contemplated marketing applications in an ICH region or at least 2 years have elapsed since the formal discontinuation of clinical development of the investigational product. However, these documents should be retained for a longer period if required by the applicable regulatory requirements or by an agreement with the Sponsor. It is the responsibility of the Sponsor to inform the investigator/institution as to when these documents no longer need to be retained.

22 PUBLICATION POLICY

The results of this study will be published. To coordinate dissemination of data from this study, a publication committee will be formed. The committee will consist of the The study PIs, interested site PIs, and appropriate ADCS and Coordinating Center personnel The committee will solicit input and assistance from the Sponsor and other investigators, as appropriate, and adhere to all ADCS Publications Policies.

23 SHARING OF FINAL RESEARCH DATA

Data from this research will be shared with other researchers pursuant to the 02/26/2003 "NIH Final Statement on Sharing Research Data". The ADCS grant contains a data sharing policy consistent with the goals of the NIH but which also respects the rights of commercial partners. The NIH policy can be found at:

<http://grants.nih.gov/grants/guide/notice-files/NOT-OD-03-032.html>

NIH believes that data sharing is important for further translation of research results into knowledge, products, and procedures to improve human health. The NIH endorses the sharing of final research data to serve these and other important scientific goals. To protect subjects' rights and confidentiality, identifiers will be removed from the data before they are shared.

25 APPENDICES

APPENDIX 1: SCHEDULE OF EVENTS

Visit Timing ^a	Day -42 to 0		Day 14 (+/- 4)	1-3 days prior to confinement	Days 21-23 (+/- 2)			
	Screening	Baseline	Phone contact	Pre-confinement ^e	Confinement			
					Admission	36-Hour Sampling	12-Hour Observation	Discharge
Informed Consent	X							
Demographics	X							
Medical and Psychiatric History	X							
CDR	X							
Logical Memory	X							
MMSE	X			X				
ADAS-Cog12		X		X				
NPI		X		X				
Physical and Neurological Examination	X	X		X	X	X		
C-SSRS	X			X				
Research Satisfaction Survey		X					X	
Vital Signs ^b	X	X		X	X	X		X
Height	X							
Clinical Safety Lab Tests ^g	X			X	X	X	PRN ^f	PRN ^f
12-Lead ECG	X							
MRI of Brain ^c	X							
Lumbar Puncture	X							
Blood Sampling for Research Labs ^h	X						X	
PK Sampling							X	
Adverse Events	X	X	X	X	X	X		X
Concomitant Medication	X	X	X	X	X	X		
Dispense Study Drug		X					X	
Dosing		X					X	
Study Drug Compliance			X	X	X			X
LP Catheter Placement							X	
Heavy Leucine Infusion							X	
CSF Catheter Sampling							X	
24-Hour Phone Follow-Up ^d	X							X

^a Refer to Section 9 for more details on visit timing and windows.

^b Vital signs will include sitting blood pressure, pulse, temperature, respiration rate, and weight, except during the 36-hour Sampling Phase of the Confinement Visit when weight will not be included.

^c An MRI of the brain will only be conducted if there is no brain MRI available from within the window specified in Inclusion Criteria.

[figure not shown]
^d Phone Follow-up should occur approximately 24-hours after completion of the LP procedure at Screening and after discharge from the Confinement Visit.

^e The Early Discontinuation Visit will contain the same assessments as the Pre-confinement Visit.

^f If safety labs are clinically indicated during the Confinement Visit, they should be sent to a local laboratory rather than the central lab.

[figure not shown]
^g Refer to Section 12.1.3 for the list of tests to be performed

[figure not shown]
^h Refer to Section 9.2 for details

APPENDIX 2: STUDY SCHEMATIC DIAGRAM

APPENDIX 3: CONFINEMENT VISIT DIAGRAM**Appendix 3.1 Confinement Visit Phase 1: Admission Diagram**

Conditions	Check
Arriving early pre-lunch	
Overnight fasting	
Study Drug Compliance	
Physical exam	
Neurological exam	
Clinical safety labs	
Vital signs	
AEs reviewed and recorded	
Con Meds reviewed and recorded	

Appendix 3.2a Confinement Visit Phase 2: Sampling – 36-Hour Observation Diagram

[figure not shown]
Appendix 3.2b Confinement Visit Phase 2: Sampling – 36-Hour Observation Schedule of Events

All sample collection times should be calculated from the start of the heavy leucine infusion

Appendix 3.3 Confinement Visit Phase 3: 12-Hour Observation Diagram

12-Hour Observation

- Observe subject for at least two hours following LP catheter removal
- Safety labs collected for local lab if clinically indicated
- Administer Research Satisfaction Survey
- Blood patch to be administered as required per subject condition in case oral intravenous fluids

Appendix 3.4 Confinement Visit Phase 4: Discharge Diagram

APPENDIX 4: SAMPLE LOW LEUCINE MENU

Low leucine meals are 1,500 mg of leucine or less a day. Individualized diet/menu is based on food preferences and coffee consumption since coffee contains leucine. Foods used for the menu are determined by availability in research kitchen and leucine values based on nutritional database values (i.e. Nutritionist Pro or Esha.com). Below is the sample of meals, beverages, and snacks menu.

	Amount	Unit	Kcal (kcal)	Protein (g)	Carb (g)	Fat (g)	Leuc (mg)
			2268.830	17.847	528.804	20.605	901.059
Breakfast			318.215	5.040	67.456	4.304	199.980
Juice, Orange, Unsweetened, Prepared from Frozen Concentrate	4.000	fl. oz.	56.025	0.847	13.421	0.075	16.185
Banana No peel (prep just before serving	101.500	g	90.335	1.106	23.183	0.335	69.020
Bread, Wheat	1.000	sl.	67.500	2.593	12.365	0.860	97.000
Jelly (includes Grape) with Leucine	25.000	g	66.500	0.038	17.488	0.005	0.000
Margarine, Spread, 60% Fat, Stick or Tub or Bottle w/ Leucine	5.000	g	26.300	0.030	0.000	2.959	0.000
Coffee, Brewed	12.000	fl. oz.	3.555	0.427	0.000	0.071	17.775
SWEET N LOW Sugar Substitute, Packet	2.000	item	8.000	0.000	1.000	0.000	0.000
Morning Snack			275.270	1.661	65.782	1.552	100.007
Crackers, Graham, Plain	14.000	g	59.220	0.966	10.752	1.414	66.500
Pear, Halves, Canned in Juice, Drained	197.100	g	98.550	0.670	25.505	0.138	33.507
Drink, Cranberry Juice Cocktail, Prepared from Frozen Concentrate w/ Leucine	8.000	fl. oz.	117.500	0.025	29.525	0.000	0.000
Lunch			477.229	3.660	114.135	3.677	199.994
Lettuce, Iceberg Leaves	50.000	g	7.000	0.450	1.485	0.070	12.500
Tomatoes, Red	15.000	g	2.700	0.132	0.584	0.030	3.750
Carrots	15.000	g	6.150	0.140	1.437	0.036	15.300
WISH BONE Salad Dressing, Italian, Light	20.000	g	23.333	0.000	2.000	1.667	0.000
Crackers, Saltine	18.000	g	75.780	1.710	13.381	1.593	117.360
Peach, Halves, Canned in Juice, Drained	141.900	g	62.436	0.894	16.418	0.043	51.084
Juice, Apple, Prepared from Frozen Concentrate w/ Leucine	8.000	fl. oz.	112.330	0.335	27.581	0.239	0.000
PEPSI Soda, Regular Cola	15.000	fl. oz.	187.500	0.000	51.250	0.000	0.000
Afternoon Snack			357.310	2.353	78.447	5.483	100.780
Cookie, Wafer, Vanilla	26.000	g	122.980	1.118	18.486	5.044	78.780
Mandarin Oranges, Canned in Light Syrup, Drained	200.000	g	122.000	0.900	32.380	0.200	22.000
Juice, Apple, Prepared from Frozen Concentrate w/ Leucine	8.000	fl. oz.	112.330	0.335	27.581	0.239	0.000
Dinner			538.445	3.264	129.832	4.007	200.294
Lettuce, Iceberg Leaves	50.000	g	7.000	0.450	1.485	0.070	12.500
Tomatoes, Red	15.000	g	2.700	0.132	0.584	0.030	3.750
Carrots	15.000	g	6.150	0.140	1.437	0.036	15.300
WISH BONE Salad Dressing, Italian, Light	20.000	g	23.333	0.000	2.000	1.667	0.000
Crackers, Saltine	22.200	g	93.462	2.109	16.503	1.965	144.744
Applesauce, Unsweetened, Canned	240.000	g	100.800	0.408	27.048	0.240	24.000
Drink, Cranberry Juice Cocktail, Prepared from Frozen Concentrate w/ Leucine	8.000	fl. oz.	117.500	0.025	29.525	0.000	0.000
PEPSI Soda, Regular Cola	15.000	fl. oz.	187.500	0.000	51.250	0.000	0.000
Evening Snack			302.360	1.870	73.153	1.582	100.004
Crackers, Graham, Plain	14.000	g	59.220	0.966	10.752	1.414	66.500
Pineapple, Canned in Juice, Drained	209.400	g	125.640	0.879	32.876	0.168	33.504
Drink, Cranberry Juice Cocktail, Prepared from Frozen Concentrate w/ Leucine	8.000	fl. oz.	117.500	0.025	29.525	0.000	0.000

APPENDIX 5: SEVERITY EVALUATION OF CHOLINERGIC ADVERSE EVENTS

Because of the potential of additive cholinergic adverse events caused by a combination of Posiphen and cholinesterase inhibitors in some subjects the severity of such adverse events should be carefully evaluated taking the criteria below into consideration (modified from "CTCAE" version 4.03.)

Adverse Event	Mild	Moderate	Severe
Nausea	Loss of appetite without alteration in eating habits	Oral intake decreased without significant weight loss, dehydration or malnutrition	Inadequate oral caloric or fluid intake; tube feeding, TPN, or hospitalization indicated
Vomiting	1 - 2 episodes (separated by 5 minutes) in 24 hrs	3 - 5 episodes (separated by 5 minutes) in 24 hrs	>=6 episodes (separated by 5 minutes) in 24 hrs; tube feeding, TPN or hospitalization indicated
Diarrhea	Increase of <4 stools per day over baseline	Increase of 4 - 6 stools per day over baseline	Increase of >=7 stools per day over baseline; incontinence; hospitalization indicated; limiting self care ADL
Anorexia	Loss of appetite without alteration in eating habits	Oral intake altered without significant weight loss or malnutrition; oral nutritional supplements indicated	Associated with significant weight loss or malnutrition (e.g., inadequate oral caloric and/or fluid intake); tube feeding or TPN indicated
Fatigue	Fatigue relieved by rest	Fatigue not relieved by rest; limiting instrumental ADL	Fatigue not relieved by rest, limiting self care ADL

Study Title: A Multicenter, Randomized, Double-Blind, Placebo-Controlled, Ascending Dose Study to Evaluate the Safety, Tolerability, Pharmacokinetics (PK) and Pharmacodynamic (PD) Effects of Posiphen® in Subjects with Early Alzheimer's Disease (AD)

Study Short Title: A Safety and PK/PD Study of Posiphen in Subjects with Early Alzheimer's Disease

Protocol Number: ADC-043-DISC (QR15001)

1 Study Eligibility

Clinical profile consistent with early AD including MCI-AD or mild AD according to the core clinical criteria outlined in the National Institute Aging (NIA) and Alzheimer's Association (NIA-AA) Guidelines
 Cerebrospinal fluid (CSF) AD biomarkers consist with AD (Beta Amyloid 42(Ab42)/Beta Amyloid 40(AB40) ratio less than 0.131 as measured by mass spectrometry) Age 55-89 (inclusive), in good health with no frailty Mini-Mental State Examination (MMSE) score between 17 – 30 (inclusive) Clinical Dementia Rating (CDR) global score of 0.5 with a memory score of 0.5 or greater, or global score of 1.0

2 Study Aims

Aim 1. Safety and Tolerability

Aim 2. PK of Posiphen/metabolites in Plasma and CSF

Aim 3. PD on fractional synthesis rate (FSR) of Beta Amyloid 40 (Ab40) in CSF

Aim 4. Feasibility of SILK in a multicenter trial

Aim 5. PD on other biomarkers in CSF including Beta Amyloid 38 (Ab38), Ab40, Ab42, Soluble Amyloid Precursor Protein alpha (sAPP α), Soluble Amyloid Precursor Protein alpha (sAPP β), total Tau

Aim 6. Cognitive and/or neuropsychiatric effects of Posiphen

3 Randomization

Subjects who have signed an informed consent and meet screening eligibility requirements will be randomly assigned to receive 60 mg Posiphen daily or placebo (with an allocation of 5 on Posiphen, 3 on placebo) by a stratified, random permuted blocked treatment assignment method, stratified by site. Following dosing of the initial 8 subjects and review of safety and tolerability, the next dose group will be 60 mg BID Posiphen or placebo (5 on Posiphen, 3 on placebo). Following the dosing of this group of 8 subjects and review of safety and tolerability, the next dose group will be 60 mg TID Posiphen or placebo (5 on Posiphen, 3 on placebo).

4 Power and Sample Size Determination

Power estimates for SILK™ studies involving measurements of FSR of Ab40 were determined by analysis of data provided by C2N, Inc., and modeled to evaluate a primary analytic goal of demonstrating a monotonic dose response relationship to Posiphen treatment. Based on a two-sided t-test for the difference between two independent means at a significance level (alpha) of 0.05 and a statistical power of 80% (1-beta), a sample size of 5 subjects in each treatment group (n active = 15) and 9 controls will provide at least 80% statistical power to detect a 27% change in the mean Ab40 FSR. The following table provides estimated power analysis to detect different effect size reductions of FSR Ab40 of 27% with 2-sided alpha and significance set at 0.05, assuming no dropouts during the SILK™ study:

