6.2 Power and Sample Size Determination

SILK™ Analyses

Power estimates for SILK™ studies involving measurements of FSR of Aβ40 were determined by analysis of data provided by C2N, Inc., and modeled to evaluate a primary analytic goal of demonstrating a monotonic dose response relationship to Posiphen treatment.

Based on a two-sided t-test for the difference between two independent means at a significance level (alpha) of 0.05 and a statistical power of 80% (1-beta), a sample size of 5 subjects in each treatment group (n.active = 15) and 9 controls will provide at least 80% statistical power to detect a 27% change in the mean Aβ40 FSR. The following table provides estimated power analysis to detect different effect size reductions of FSR Aβ40 of 27% with 2-sided alpha and significance set at 0.05, assuming no dropouts during the SILK™ study:

Table 2. Estimated Power Analysis

	n.active= 12	n.active= 15	n.active= 18
n.cont= 8	0.783	0.822	0.848
n.cont= 9	0.812	0.851	0.876
n.cont= 10	0.836	0.874	0.898

This serves as justification for our sample size estimate of 24. We expect that if dropouts are to occur, they will occur before the SILK™ studies at day 23-25 and can be replaced to allow the full sample size of 24 for SILK™ being achieved.

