6.5 SILK™ Analysis

In SILK™ studies, the mass spectrometry data will be used to calculate the fraction of labeled A β for A β 38, 40, and 42 during 36 hours after administration of study drug for each subject, as described. The FSRs will be calculated by fitting a line to this data. FSRs for treated and untreated subjects will be compared by analysis of variance (ANOVA). The percentage of newly synthesized and degraded A β will be estimated over 36 hours by multiplying the mass spectrometry concentration of A β by the % of A β that contains ¹³C₆-leucine at each time point. This will be used to estimate the AUC of the drug for decreasing the amount of newly produced A β ([Bateman 2009](#)).

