The primary outcome measure of Fractional Synthesis Rate (FSR) of Abeta 40 will be compared across all Posiphen treated groups to placebo. A linear regression model will be used to evaluate treatment effects on the FSR Abeta 40, with age and gender as covariates. Quality control of samples for the FSR 40 will be ascertained to determine sufficiency of the sample values prior to this regression analysis.

A secondary analysis will test for possible dose group by treatment interaction.

Exploratory analyses will include PK AUC correlation to Abeta 40 FSR and other SILK measured analytes (Abeta 38, 42, ratio 42/40, total Abeta peptides) including absolute synthesis and clearance.

C2N will analyze Beta Amyloid 40 (Ab40).

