To evaluate the PK PD relationships, trough levels of Posiphen at day 21 (time 0) will be examined as a predictor of change in the CSF levels of each of these biomarkers between baseline and day 21. A linear regression model will be used to predict the change in CSF analyte with the covariates of trough PK, age, and gender. Other PK measures will be similarly evaluated including AUC, and Cmax.

In a secondary analysis to evaluate the effect of dose, we will use a similar regression model with terms for placebo and each dose group as predictors, including age and gender as covariates.

5.2.3 Aim 3

To assess whether there are short-term cognitive and/or neuropsychiatric effects of Posiphen in subjects with early AD, either positive or negative on ADAS-Cog12, MMSE, Neuropsychiatric Inventory (NPI).

These cognitive and neuropsychiatric measures will be compared between Posiphen and placebo using multiple linear regression. This methodology will allow the comparison of mean change scores between the active and placebo groups while initially adjusting for covariates; age, gender, treatment arm and baseline MMSE. Dose effects will be assessed as part of this analysis to investigate trends. The effects of ApoE genotype on these clinical outcome measures will also be explored as a tertiary analysis.

C2N will analyze Beta Amyloid 38 (Ab38), Ab40, and Ab42. The ADCS Biomarker Core will analyze Soluble Amyloid Precursor Protein alpha (sAPP α), Soluble Amyloid Precursor Protein alpha (sAPP β), and total Tau protein.

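### The FSR power of 0.851 is attached to a monotonic dose-response goal, but it is power for pooled Posiphen versus placebo, and no FSR analysis tests ordered dose

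*SAP*

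**What the plan says.** - **Goal.** SAP 4 and Protocol 6.2 use the same sentence: power was "modeled to evaluate a primary analytic goal of demonstrating a monotonic dose response relationship to Posiphen treatment".
- **Calculation.** The next sentence in SAP 4 reads "Based on a two-sided t-test for the difference between two independent means at a significance level (alpha) of 0.05". Protocol 6.2 then states that "a sample size of 5 subjects in each treatment group (n.active = 15) and 9 controls will provide at least 80% statistical power" for a 27% change. The power table in each document is indexed only by the numbers of active and control subjects, and it is offered as the justification for 24 subjects.
- **Primary FSR analysis.** SAP 5.1.3 says that FSR "will be compared across all Posiphen treated groups to placebo", by linear regression with age and gender. Protocol 6.5 plans an ANOVA of treated against untreated subjects.
- **Dose-related FSR analyses.** SAP 5.1.3 adds: "A secondary analysis will test for possible dose group by treatment interaction". It does not say how dose group is coded. It also says: "Exploratory analyses will include PK AUC correlation to Abeta 40 FSR".
- **Other CSF biomarkers.** SAP 5.2.2 says that, for the effect of dose, "we will use a similar regression model with terms for placebo and each dose group as predictors". No such model is listed for FSR.

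**The concern.** The power sections name one question, whether effect rises with dose, and answer another, whether Posiphen differs from placebo on average. Dose does not enter the power table or the primary FSR analysis. An unordered interaction test responds to unequal effects in any direction, so it cannot show monotonicity. The AUC correlation concerns exposure and is exploratory.

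Two misreadings are at stake. A reader may take 0.851 as the chance of showing a dose response. Later, a non-significant interaction may be read as evidence that QD, BID and TID act alike, when the test had little chance of separating them. This matters because the protocol introduction says the SILK result is meant to guide further development, and its dose-selection rationale uses several regimens to study the PK/PD relationship.

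**Working it through.** **1. Reproduce the stated power.** Inputs from Protocol 6.2 and SAP 4: two-sided alpha 0.05, 15 active, 9 control, 27% change, power 0.851. No SD is given, so the standardized effect d is solved from this cell.

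- Power = P(|T| > t₀.₉₇₅,df), with T noncentral t, df = n₁ + n₂ − 2 and noncentrality d/√(1/n₁ + 1/n₂).
- For 15 v 9: df = 22, critical value 2.074. Power 0.851 gives d = 1.324, noncentrality 3.14.
- Implied SD = 27/1.324 = 20.4% of the placebo mean.
- This one d reproduces all nine cells within 0.001. For example, 12 v 8 gives 0.7833 (stated 0.783) and 18 v 10 gives 0.8981 (stated 0.898). A one-sided test calibrated to the same cell gives 0.793 at 12 v 8, and a normal approximation gives 0.792. The table is a pooled two-sided t-test.

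**2. Power of the planned and possible dose analyses at the same SD.** The layout is 3 placebo and 5 active per cohort (9/5/5/5 overall), without covariates. Reductions at QD/BID/TID are assumed shapes, because the documents give none. The pooled test, the slope including placebo and the 1-df interaction were simulated with 200,000 replicates.

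| Reduction at 60/120/180 mg (%) | Pooled v placebo | Slope on 0/60/120/180 | Slope, 15 actives only | Interaction, 2 df / 1 df |
|---|---|---|---|---|
| 27/27/27 | 0.85 | 0.66 | 0.05 (null) | 0.05 (null) |
| 18/27/36 | 0.83 | 0.90 | 0.25 | 0.10 / 0.13 |
| 13.5/27/40.5 | 0.80 | 0.95 | 0.49 | 0.17 / 0.23 |
| 9/18/27 | 0.48 | 0.67 | 0.25 | 0.10 / 0.13 |

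For the non-monotone shape 20/27/20, the slope including placebo is significant with probability 0.50.

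**3. Closed-form checks.**

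- *Active-only slope*, equal steps, n per dose: noncentrality = (step/SD)√(2n), df = 3n − 2. Step 9, n = 5: (9/20.39)√10 = 1.396, power 0.25. Step 13.5: 2.094, power 0.49. Power 0.80 needs a step of about 19.5 points (39 points from lowest to highest dose), or n = 21 per dose at a 9-point step.
- *2-df interaction*: each cohort effect has weight 1/(1/5 + 1/3) = 1.875, so λ = 1.875 × 2 × (step/SD)², with F on 2 and 18 df. Step 9: λ = 0.73, power 0.10. Step 13.5: λ = 1.64, power 0.17.
- *One dose v all placebo (5 v 9)*: noncentrality 1.324/√(1/5 + 1/9) = 2.374, df = 12, power 0.59 at 27%. Power 0.80 needs a 34.7% reduction.
- *95% CI half-width for one dose v placebo* in a four-group model: 2.086 × 20.39 × √(1/5 + 1/9) = 23.7 percentage points of the placebo mean.

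**4. Sensitivity to the SD.** At CV 18%, d = 27/18 = 1.50: pooled power 0.92, one dose v placebo 0.69. At CV 23%, d = 27/23 = 1.174: pooled 0.76, one dose v placebo 0.49.

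**The case against.** - **The test is named in the next sentence.** A statistical reader can see what 0.851 refers to, and Aim 3 makes no claim about monotonicity. Apart from one clause, the aim, sample size, table and primary analysis all fit active versus placebo. This stands as a reason to leave the primary test alone. It does not make the clause correct, and the clause appears in both documents.
- **No stated power is not the same as no power.** If placebo counts as dose zero, a slope test with 24 subjects reaches 0.95 for 13.5/27/40.5, more than the pooled test. This stands: the design could support a trend test under some shapes. But no such test is specified for FSR, and the same slope is significant 66% of the time for a flat 27% effect and 50% for a non-monotone one. A significant result would not establish ordering.
- **Counting only the active doses is a stricter reading than the documents impose.** This is fair, so both readings are shown above.
- **Secondary and exploratory analyses often have no power figure.** This is true, but here the documents call the dose response the primary analytic goal.
- **The SD and the shapes are assumptions.** This also stands. The mismatch itself does not depend on them.

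**Conclusion.** The point holds. The arithmetic of the power table is right, but it answers a different question from the one named above it. The 0.851 is power for the pooled contrast when reductions average about 27% with little spread across doses. It falls to 0.80 for 13.5/27/40.5 and to 0.48 if 27% is reached only at the top dose of a 9/18/27 gradient. For the spacings tried, the planned interaction test has power 0.10 to 0.23, and ordering among the three active doses has power 0.25 to 0.49.

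The mismatch rests on the text alone. The figures rest on a back-solved CV of 20.4%, equal variances, no covariates, no dropout and the assumed shapes. The point should be fixed, but it does not threaten the primary FSR comparison.

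**What to change.** 1. **Protocol 6.2 and SAP 4.** State that 0.851 is power for pooled Posiphen against placebo at a uniform 27% reduction. Then either delete the monotonic-goal statement, or keep it with the graded and single-dose figures and the SD assumption behind them.
2. **SAP 5.1.3.** Keep the pooled contrast as primary. Keep the interaction test and state how dose group is coded. Add a secondary 1-df trend of FSR on total daily dose (0/60/120/180 mg), adjusted for age and gender. Report dose-specific estimates against placebo with 95% CIs from a dose-group model like the one already planned in SAP 5.2.2.
3. **Interpretation.** State in advance that a significant slope including placebo does not by itself show ordering among doses, that a non-significant interaction is not evidence of equal effects, and that the active-only slope is descriptive. Label the added tests as secondary, since they add p-values.

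The cost is wording in two power sections and one or two extra models, with no extra patients. The stated support for a dose-response claim becomes less favourable, and the dose-specific intervals will be wide, at about ±24 points.
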